2.3 Sample size determination

The primary aim of the study is to demonstrate that patients in the "Drug target biomarker" group (Group 1) will have a higher response rate than the "No drug target biomarker" groups (Group 2 and 3)- see section 2.2 for trial diagram.

Using change in CDAI score from baseline (delta CDAI) as the primary outcome, a difference in delta CDAI between the two comparison groups of 10, with a Standard Deviation of 14.34. These are the values that were observed when analysing the difference in delta CDAI between biomarker positive and biomarker negative patients treated with MTX in the PEAC study. Although PEAC patients were not treated with Abatacept, this comparison is expected to be even more in favour of the biomarker positive group using Abatacept together with MTX. Thus, basing the power calculation on the PEAC observed difference is a conservative assumption.

With these assumptions, 90 patients would be needed to detect a significant difference of 10 in delta CDAI with 90% power. Since this would only be for Group 1 and Group 3 (45 patients each), a total of 180 patients would be sufficient for 90% power in the whole trial (Figure 1 Section 2.6). If we assume a 5% dropout rate and also account for an expected 5% of patients that have insufficient RNA for the Nano-string analysis (based on results from the STRAP trial), 200 patients in the whole trial would be sufficient to detect a significant difference (Group 1 vs Group 3) of 10 in delta CDAI with 90% power.

All power calculations were performed using the "twomeans" package in STATA, version SE 18.

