2.4 Randomisation

Randomisation will take place when all the screening procedures and the biopsy visit are completed, and the patient is eligible for enrolment in the study. The randomisation in the study will be applied using simple randomisation, with equal allocation ratio (1:1). All patients with sufficient RNA for analysis will be randomised using simple randomisation (1:1 allocation ratio) into the Control or the Treatment arm according to biomarker arm.

Patients allocated to the control arm of the study, will be subsequently randomised again using simple randomisation with equal treatment allocation ratio (1:1) to Abatacept and Methotrexate therapy or placebo and Methotrexate therapy.

Once the biopsy sample has been received by the central laboratory, patients will be stratified into 2 groups, CD80/CD86 positive (biomarker+) or CD80/CD86 negative (biomarker-) and randomised 1:1 to receive either Abatacept and Methotrexate therapy or placebo and Methotrexate therapy.

3. General Analysis Definitions

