4.7 General considerations

For each treatment group and biomarker, the following will be presented:

- Number and percentage of subjects screened, not randomised/assigned treatment, randomised/assigned treatment, randomised/assigned treatment and not started treatment, discontinued, and completed.
- Number and percentage of subjects randomised at each site.
- Number and percentage of subjects in each analysis set (ITT) overall and by visit.
- Number and percentage of subjects excluded from each analysis set by reason for exclusion.
- Number and percentage of withdrawals (withdraw consent to any further participation in the trial) and treatment cessation, by reason for discontinuation and visit.

5. Interim analysis and timing for analysis

No interim analysis is planned for the current trial. However, the TSC will review the accruing trial data every year during the recruitment phase of the study and assess whether there are any safety issues that should be brought to participants' attention or any reasons for the trial not to continue. TSC reports will consist of an open report where the accrual data will be described without any information on the arm patients have been allocated to, and a closed report where any safety issues by treatment arm will be presented. No stopping rule will be used. See section 9 for further detail. The trial data will be analysed following database lock.

6. Efficacy analysis

The listed measures in Table 2 are to be used in the analyses. The analyses will be carried out in STATA 18 or higher.

In hypothesis testing, the null hypothesis is rejected at (two-sided) significance level 0.05 unless otherwise specified.

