6.3 Analysis of exploratory endpoints

The robustness of the results on the primary and secondary endpoints will be assessed using the exploratory outcomes as presented in the table below.

Table 2: List of exploratory outcomes that are used in the analyses.

Logistic regression with the treatment, and study as factors will be used. Exact logistic regression will be considered if the sample size is too small for a regular logistic regression and/or if some of the cells have no observations. Separate analysis will be performed for biomarker/no biomarker using the ITT population. Statistical analysis Mixed-effects modelling will be performed with treatment, time and patient as factors, and baseline score as covariate. If the assumptions of the Mixed-effects modelling are not met, the data will be analysed GEE methods.	
Mixed-effects modelling will be performed with treatment, time and patient as factors, and baseline score as covariate. If the assumptions of the Mixed-effects modelling are not met, the	
patient as factors, and baseline score as covariate. If the assumptions of the Mixed-effects modelling are not met, the	
Statistical analysis	
requency and percentage of each outcome will be reported by treatment and biomarker using the safety analysis set (SAF).	
Statistical analysis	
Pearson or Spearman (rank) correlation coefficients will be used to assess the correlation between two continuous measures depending on normality.	
T-test or Mann-Whitney test will be used to assess the association	

Association between disease
outcome (binary variables),
treatment group and ultrasound
measure of inflammation
Association between disease
outcome (binary variables),
treatment group and disability
Association between disease outcome
(continuous variables), treatment group
and synovial histology (binary variables)
Association between disease outcome
(continuous variables), treatment group
and synovial histology (continuous
variables)
Association between disease outcome
(continuous variables), treatment group
and Ultrasound measure of inflammation
Association between disease outcome
(continuous variables), treatment group
and disability

Two-way analysis of variance or Friedman's two- way analysis of variance will be used to assess the association between two categorical (including binary) measures and a continuous outcome depending on normality.

Log linear model will be used to assess the association between three binary outcomes.

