6.5 Assumptions for analysis

The independence of observations (patients) is assumed within centres, as well as between centres However, the intraclass correlation (ICC) between centres will be tested, if it is significant, a mixed-effects models regression will be used with random effects for centres (and fixed treatment effects).

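### SAP 6.3 names Friedman's test as the non-normal fallback for two between-patient factors, a layout on which that test is not defined (minor; exploratory analyses only)

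*SAP*

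**What the plan says.** Table 2 in SAP Section 6.3 lists exploratory association analyses and the methods for them. One method sentence reads "Two-way analysis of variance or Friedman's two- way analysis of variance will be used" and continues "to assess the association between two categorical (including binary) measures and a continuous outcome depending on normality". Two-way ANOVA is thus the method when normality holds, and Friedman's test when it does not.

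The listed row that fits this description is disease outcome ("continuous variables), treatment group") "and synovial histology (binary variables"): one continuous outcome and two categorical factors.

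Two other places fix the data structure. Section 2.4 has patients "randomised 1:1 to receive either Abatacept and Methotrexate therapy or placebo and Methotrexate therapy", so each patient receives one treatment. Section 6.5 states: "The independence of observations (patients) is assumed within centres, as well as between centres". No block, matching or repeated measure is defined for this analysis, and no extension of Friedman's test to cells with several patients is named.

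**The concern.** Although it is often called a two-way analysis, Friedman's test is the rank counterpart of a randomised-block or repeated-measures layout. It is not the rank counterpart of a factorial ANOVA on independent patients. One factor serves only as the block, and the other is compared within it. Moving from two-way ANOVA to Friedman's test therefore changes the question as well as the distributional assumption: ANOVA can test both factors, whereas Friedman's test covers only one.

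At stake is part of exploratory endpoint 5 (Section 3.3.3), which relates synovial histology to drug response and outcome. Section 6.3 says the exploratory outcomes serve to assess the robustness of the primary and secondary results. Section 1 commits the main papers to this strategy and requires deviations to be justified. If normality failed, the statistician would have to choose a replacement method after seeing the data, or force a test that does not fit.

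**Working it through.** **1. The plan's own figure.** No number is attached to the Friedman sentence. The only design figure is the sample size in Section 2.3, based on "a difference in delta CDAI between the two comparison groups of 10, with a Standard Deviation of 14.34", with 90% power. At two-sided 5%, the normal approximation gives n per group = 2 x (1.960 + 1.282)² x 14.34² / 10² = 43.2, so 44. By the t-test, 45 per group gives 90.5% power. Allowing 5% + 5% for losses, 180 / (1 - 0.10) = 200. The stated 90, 180 and 200 reproduce. They are used below only to set the scale of a simulation.

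**2. Does the test fit the data?** Friedman's test needs b blocks, each holding one value for each of k compared levels.
- Patients as blocks: each patient has one treatment and one histology class (Section 2.4 for treatment; histology is a patient-level class). Every block lacks all but one level, so nothing can be ranked within it.
- Histology class as block: each treatment-by-histology cell holds many independent patients, so the standard one-value-per-cell statistic is not defined.

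**3. What if it were forced?** This is a hypothetical that the SAP does not propose: collapse each cell to one value, such as its median. With rank sums R, the statistic is Q = 12 / [b k (k + 1)] x ΣR² - 3 b (k + 1). It is largest when all blocks rank the levels identically, giving Q max = b(k - 1). The smallest chi-square p is the upper tail at Q max on k - 1 degrees of freedom. The smallest exact p is (k!)^(1 - b).

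Section 6.3 does not say whether treatment group has two levels (abatacept, placebo) or four (Groups 1 to 4, as in Section 2.1), so both are shown with binary histology.

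| Collapsed layout | b | k | Q max | Smallest chi-square p | Smallest exact p |
|---|---|---|---|---|---|
| 2 treatments within 2 histology classes | 2 | 2 | 2 | 0.157 | 0.50 |
| 4 groups within 2 histology classes | 2 | 4 | 6 | 0.112 | 0.042 |
| 2 histology classes within 4 groups | 4 | 2 | 4 | 0.0455 | 0.125 |

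Check of the first row: the rank sums are 2 and 4, so Q = 12/12 x (4 + 16) - 18 = 2.

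The opening of Section 6 sets the threshold: "the null hypothesis is rejected at (two-sided) significance level 0.05 unless otherwise specified". The 2x2 layout cannot meet it under either reference distribution, however many patients are enrolled. Each four-group layout can meet it under one reference distribution and not under the other.

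**4. Simulation of the 2x2 case.** The simulation used 2,000 trials with 45 patients per cell (180 in all), skewed (exponential) errors with SD 14.34 and a treatment effect of 10. Friedman's test on cell medians rejected in 0% of trials. A patient-level two-way ANOVA on ranks rejected in about 100%. The skewed errors are an assumption, since the SAP gives no distribution for its outcomes.

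**The case against.** The SAP nowhere says that patients would be collapsed to cell medians. More realistically, the statistician would find that the named test cannot be run and would use another. Section 1 leaves room for accepted practices such as transformation and provides for justified deviations, so transforming the outcome and keeping the two-way ANOVA is open under the plan as written. Only a few exploratory rows are concerned. The primary analysis is a mixed-effects model with its own GEE fallback (Section 6.1.1), and continuous secondary outcomes also use mixed-effects models (Section 6.1.2). All of this stands, and it limits the point to a minor one. It does not make the named test applicable.

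A reader might infer more than the documents support:
- That these analyses could never reach significance. This holds only for the hypothetical collapsed 2x2 layout. With four groups, exact p = 0.042 or chi-square p = 0.0455 is attainable.
- That endpoint 5 would be left with no valid test. Section 6.3 also names Pearson or Spearman correlation, t-test or Mann-Whitney, log-linear models and chi-square or Fisher tests for other rows. The Friedman rule covers only two categorical measures with a continuous outcome.
- That the fallback is likely to be used. The SAP gives neither outcome distributions nor a normality criterion, so the frequency is unknown.
- That an interaction test is required. The SAP asks only for association. An interaction estimate would be useful, but its absence is not an error.

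**Conclusion.** The point holds as a minor one. The stated rule is wrong as written: Friedman's test requires blocked or repeated data, and Section 6.3 applies it to two between-patient factors in independent patients. This rests only on Sections 2.4, 6.3 and 6.5 and on the definition of the test. The figure of 0.157 rests further on two assumptions, a two-level treatment factor and collapsing to one value per cell. It shows what forcing the test would cost and does not predict what will be done. The consequence arises only when normality is judged to fail. No primary or secondary conclusion, sample size or safety result changes.

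**What to change.** In Section 6.3, delete Friedman's test and name a between-patient two-factor method for when normality fails. Two suitable choices are the same two-factor linear model with heteroscedasticity-robust (HC3) or bootstrap standard errors, or a two-factor ANOVA on aligned ranks. The same edit could state whether treatment group means two treatments or Groups 1 to 4. The cost is one sentence in the SAP, with no extra data and no burden on patients. Making the change before unblinded analysis avoids choosing the method after the results are visible.

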6.4 Generated variables

The generated variables are ACR20, ACR50, ACR70, CDAI, DAS28, HAQ, SF-36, FACIT-Fatigue, ESS and EQ-5D-5L scores.

Instrument	Transformation
ACR Improvement ⁷	
20%	
50%	Refer to Protocol Section 9.8.1
70%	
CDAI ⁸	Refer to Protocol Section 9.8.2
DAS28 ⁹	Refer to Protocol Section 9.8.2
HAQ ¹⁰	Refer to Protocol Section 9.8.3
SF-36 ¹¹	Refer to Protocol Section 9.8.4
FACIT-Fatigue ¹²	Refer to Protocol Section 9.8.5
ESS ¹³	Refer to Protocol Section 9.8.6
EQ-5D-5L scores ¹⁴	Refer to Protocol Section 9.8.7

6.5 Assumptions for analysis

The independence of observations (patients) is assumed within centres, as well as between centres However, the intraclass correlation (ICC) between centres will be tested, if it is significant, a mixed-effects models regression will be used with random effects for centres (and fixed treatment effects).

6.6 Methods for handling dropouts, missing data and outliers

6.6.1 Handling of dropouts

The number of dropouts before 16 weeks will be monitored by treatment group. This will be reviewed at TSC meetings. If one treatment causes considerably higher dropouts, further investigation will be carried out to seek the explanations.

6.6.2 Handling of missing data

The missing values in primary outcome will be considered separately from other variables.

It is rare that the primary outcome is missing, but if so, the CDAI response at another visit will be used as the primary outcome. If a patient stops treatment before reaching visit 7 (when the primary endpoint is obtained) but CDAI response is available at visit 6, the CDAI at visit 6 will be used for the primary endpoint. When more than 5% of primary endpoint data is missing under other circumstances, Missing data for essential outcome variables and their subcomponents will be handled by multiple imputation by chained equation (MICE), incorporating longitudinal datapoints. Imputation will be performed five times and the mean (or median, if a particular variable is not Gaussian) result of imputation will be used to replace missing values. Imputed values will be checked for excessive variability across the five imputation runs assuming data are missing at random (MAR). Multiple imputations will be implemented using STATA (version 18 or higher). The performance of the imputations will be examined through the convergence and marginal distributions. Five imputations will be produced and the pooled results of the 5 analyses will be presented.

For questionnaires (SF-36, HAQ, EQ-5D-5L, ESS and FACIT fatigue), the database will produce the final scores. The missing component score values will be imputed using the same technique as describe above.

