3.2 Study populations

3.2.1 ITT population

ITT population includes all the patients who were enrolled in the trial and were randomised/assigned treatment according to biomarker. All patients will be analysed according to the randomisation/treatment allocation including any withdrawals after randomisation/treatment allocation.

There are two types of withdrawal defined; full withdrawal from the study (the patient does not attend any further visits) or withdrawal from trial treatment (treatment cessation). The data collection and follow up requirements are specified in Sections 15 of the trial protocol.

ITT analysis will be used for all analyses except for the safety analysis in Section 14.9.

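### Section 6.6.2 puts an earlier CDAI value in place of week 16, by a rule that is loosely triggered, open in its choice of visit, and unnecessary in the planned mixed model

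*SAP*

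**What the plan says.** SAP Section 6.6.2 describes a missing primary outcome as rare and continues: "if so, the CDAI response at another visit will be used as the primary outcome". It names neither the visit nor an order of preference. The next sentence covers patients who stop treatment before visit 7 and have a CDAI response at visit 6. For them, "the CDAI at visit 6 will be used for the primary endpoint". Multiple imputation by chained equations, assuming MAR, is then kept for the case where more than 5% of the primary endpoint is missing in other circumstances.

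Three other places bear on this:

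- **Section 3.1.2** makes baseline visit 3 (week 0), with visits every four weeks after it. **Section 6.1.1** makes week 16 visit 7. Visit 6 is therefore week 12.
- **Section 6.1.1** plans a mixed-effects model with continuous time. CDAI is measured at weeks 0, 4, 8, 12 and 16, and baseline enters as a covariate.
- **Section 3.2.1** states: "All patients will be analysed according to the randomisation/treatment allocation including any withdrawals after randomisation/treatment allocation". It separates full withdrawal from the study, after which no visits are attended, from stopping trial treatment.

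**The concern.** There are four difficulties.

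1. **Trigger.** The visit-6 sentence depends on stopping treatment and on visit 6 being available. It does not require week 16 to be missing. Because Section 3.2.1 separates stopping treatment from leaving the study, a patient can stop treatment and still have a week-16 CDAI. Read literally, the rule would replace that value with the week-12 one, which goes against the intent of an ITT analysis of the week-16 outcome.
2. **Choice of visit.** Week 4, 8 or 12 would each satisfy the general rule, so the choice could be made after the data are seen.
3. **Fit with the model.** Week 12 is already an outcome row. Moving its value to week 16 mis-times it in a model where time is continuous. Copying it makes one measurement serve at two times and imposes no change over the last four weeks.
4. **Uncertainty.** A substituted value is analysed as if it had been observed.

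At stake is a primary contrast in which some patients contribute week 16 and others an earlier value. If the share or timing of stopping differs between Group 1 and Group 3, the contrast is biased.

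**Working it through.** **Inputs from the SAP**

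- Section 2.3: "a difference in delta CDAI between the two comparison groups of 10, with a Standard Deviation of 14.34", and "90 patients would be needed to detect a significant difference of 10 in delta CDAI with 90% power", that is 45 in each of Groups 1 and 3.
- Opening of Section 6: "the null hypothesis is rejected at (two-sided) significance level 0.05 unless otherwise specified".
- Section 2.3: "If we assume a 5% dropout rate and also account for an expected 5% of patients that have insufficient RNA".

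**Reproducing the plan's figures**

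- Normal approximation: n per group = 2 × 14.34² × (1.960 + 1.282)² / 10² = 43.2, rounded up to 44.
- Two-sample t-test with the noncentral t distribution: 45 per group, 90 in total, with power 0.905. The standard error is 14.34 × √(2/45) = 3.02.
- Whole trial: 180 / 0.90 = 200. Applying the two 5% losses in turn gives 180 / 0.95 / 0.95 = 199.4, also 200.

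The sample size is reproduced, and this point does not dispute it.

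**Effect of substituting week 12**

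Let d be the share of a group whose week-12 value stands in for week 16, and D12 the true week-12 difference. With the same d in both groups, the expected difference is 10 × (1 − d) + D12 × d. The SAP gives neither d nor D12, so both are assumptions. The 5% dropout rate is the nearest planning figure for d. Power is from the noncentral t distribution at 45 per group.

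| Assumed D12 | d | Difference | Power |
|---|---|---|---|
| any | 0% | 10 | 0.905 |
| 7.5 (linear accrual: 10 × 12/16) | 5% | 9.875 | 0.898 |
| 7.5 | 10% | 9.75 | 0.891 |
| 7.5 | 20% | 9.50 | 0.875 |
| 9.5 (most of the effect reached by week 12) | 5% | 9.975 | 0.904 |
| 9.5 | 20% | 9.90 | 0.900 |

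**Unequal stopping**

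Assume mean week-16 changes of −20 in Group 1 and −10 in Group 3, linear in time. The week-12 means are then −15 and −7.5.

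- 10% substituted in Group 1 only: 0.9 × (−20) + 0.1 × (−15) = −19.5. The difference is 9.50, power 0.875.
- 10% substituted in Group 3 only: 0.9 × (−10) + 0.1 × (−7.5) = −9.75. The difference is 10.25, power 0.918.

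**Worsening after stopping**

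If 5% to 10% of a group stop after week 12 and their true CDAI rises by 5 to 10 points by week 16, that group's mean looks too favourable by 0.05 × 5 = 0.25 to 0.10 × 10 = 1.0 points. The contrast moves only by the between-group difference in that amount. These rates and changes are also assumptions.

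**Limit of the check**

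The figures are for a two-group comparison of change at week 16, as in Section 2.3. They do not measure what a duplicated row does to the slope, covariance or standard error of the mixed model.

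**The case against.** Several stronger readings are tempting, and the document does not support them.

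- **That the rule contradicts the ITT definition.** Sections 3.2.1 and 6.1.1 define ITT by who is included and by allocated arm. Using a week-12 value drops no patient and changes no arm. The tension is with the intent of ITT, and only on the literal reading of the trigger.
- **That observed week-16 values will certainly be overwritten.** The sentence stands under missing data and follows one about a missing primary outcome. The imputation sentence after it refers to data missing in other circumstances, which implies that the visit-6 case is itself one of missing data. The narrower reading is therefore available. Whether patients who stop treatment attend week 16 is left to the protocol, which is not shown.
- **That one value is necessarily counted twice.** The SAP does not say whether the value is copied or moved. If it is moved, the fault is mis-timing only.
- **That baseline could be carried forward.** The text speaks of a CDAI response, the endpoint is change from baseline, and baseline is a covariate. Baseline is not a plausible source, although week 4 remains possible.
- **That the replacement is an on-treatment value.** A patient who stopped before week 12 has an off-treatment week-12 value.

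It is also fair to say that the plan expects few missing outcomes and that the effect is small at its dropout rate.

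These objections narrow the point but do not remove it. The visit is still not fixed and the trigger can still be read two ways. The substituted value is still placed at the wrong time and treated as observed. The planned model does not need it, because it can use a patient's observed visits without week 16 under MAR, the assumption Section 6.6.2 already makes for imputation.

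**Conclusion.** The point holds as a fault in the stated method and should be corrected before unblinded analysis. It does not threaten the sample size, and its likely numerical effect is small. With linear accrual and 5% substituted in both groups, the difference is about 9.9 instead of 10 and power about 0.90 instead of 0.905. If most of the effect is present by week 12, the loss is negligible. With 10% substituted in one group only, the assumed example gives 9.50 or 10.25, so the direction cannot be predicted. All of these figures rest on assumed stopping rates and time courses that the SAP does not give. Double use of a measurement is conditional on copying, and replacement of an observed value is conditional on the literal reading.

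**What to change.** In Section 6.6.2:

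- Delete both substitution sentences from the primary analysis.
- State that every observed CDAI is analysed at its actual visit, whatever the patient's treatment status.
- State that a missing week-16 CDAI stays missing and is handled under MAR by the Section 6.1.1 mixed model, or by multiple imputation with the analyses properly pooled. The section currently describes both replacing missing values with the mean or median of the imputations and pooling the five analyses. Only pooling carries the imputation uncertainty into the result.
- If carry-forward is kept, label it a sensitivity analysis and name the visit and the order of choice. A sensitivity analysis that departs from MAR would be a useful but optional addition.

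The cost is SAP wording and minor analysis work. The change uses whatever CDAI values are collected and leaves the sample size as it is.

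### SAP section 6.6.2 gives two incompatible rules for the same missing data, and one of them, averaging five imputations into a single dataset, understates standard errors

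*SAP*

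**What the plan says.** SAP section 6.6.2 handles a missing primary outcome in steps.

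- A CDAI value from another visit is used first. For a patient who stops treatment before visit 7, a visit 6 value stands in.
- "When more than 5% of primary endpoint data is missing under other circumstances", missing values of essential outcome variables and their subcomponents are to be "handled by multiple imputation by chained equation (MICE), incorporating longitudinal datapoints", under a missing-at-random assumption.
- Imputation is run five times, and "the mean (or median, if a particular variable is not Gaussian) result of imputation will be used to replace missing values".
- The paragraph closes: "Five imputations will be produced and the pooled results of the 5 analyses will be presented".

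The next paragraph covers SF-36, HAQ, EQ-5D-5L, ESS and FACIT fatigue: "The missing component score values will be imputed using the same technique as describe above". HAQ-DI and SF-36 are secondary endpoints in section 3.3.2.

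**The concern.** The two closing instructions describe different procedures. Filling each gap with the mean or median of five draws gives one dataset and one analysis, so no five analyses remain to be pooled. No sentence ranks the rules or assigns them to different variables. Two statisticians who each followed the SAP faithfully could report different standard errors, confidence intervals and p-values for the primary endpoint.

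The averaging rule is also invalid in itself. It is single imputation. The filled-in values vary too little, and the disagreement between imputations, which multiple imputation exists to carry into the standard error, is discarded. The result is intervals that are too narrow and a true type I error above the two-sided 5% of section 6.

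**Working it through.** **The plan's own figure.** Section 2.3 gives a difference of 10, SD 14.34, 90% power and 45 per group. Section 6 gives two-sided alpha 0.05. Normal approximation: n = 2 × (1.96 + 1.2816)² × 14.34² / 10² = 43.2, so 44 per group. The noncentral t gives 89.9% power at 44 and 90.5% at 45. The stated 45 per group reproduces and is used below.

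**Assumptions that the SAP does not supply.** The share p still missing when imputation is applied; the correlation ρ between the outcome and an earlier measurement used to impute it; values missing completely at random in the formulas; a two-group t-test in place of the planned mixed-effects model. The number of imputations is m = 5, as planned.

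**Formulas.** With complete data, SE₀ = 14.34 × √(2/45) = 3.02.

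1. Averaging five draws leaves only one fifth of the residual variance in each filled-in value. The reported squared SE is about SE₀² × A, with A = 1 − (1 − 1/5) p (1 − ρ²).
2. The actual sampling variance of that estimate is about SE₀² × T, with T = 1 + (1 + 1/5)(1 − ρ²) p/(1 − p). Rubin's rules estimate the same quantity.
3. Type I error is about 2 × [1 − Φ(1.96 × √(A/T))].

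**Worked case, p = 0.20, ρ = 0.6.** A = 1 − 0.8 × 0.20 × 0.64 = 0.898, so the reported SE is 3.02 × √0.898 = 2.86. T = 1 + 1.2 × 0.64 × 0.25 = 1.192, so the true SE is 3.02 × √1.192 = 3.30. The ratio is 0.868 and type I error about 8.9%. Simulation (4,000 null trials) gave a reported SE of 2.86, an empirical SD of 3.34 and 9.2% rejection. Rubin's rules gave SE 3.32 and 4.8%.

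**Range over ρ = 0.3 to 0.7.** Five of 90 is the smallest count above the trigger (5/90 = 5.6%; 4/90 = 4.4%).

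| Share missing | Reported / true SE (formula) | Type I error, formula | Type I error, simulation |
|---|---|---|---|
| 5/90 | 0.95-0.97 | 5.7-6.3% | 5.4-5.7% (run at 5% missing) |
| 10% | 0.91-0.95 | 6.3-7.5% | 6.6-7.9% |
| 20% | 0.82-0.89 | 8.0-10.8% | 8.2-10.7% |

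The simulation column comes from 6,000 null trials per setting with data missing at random. Rubin's rules with m = 5 gave 4.6-5.4% on the same data at 10-20% missing. A separate set of 4,000 null trials per setting, missing completely at random with ρ = 0.3, 0.6 and 0.8, gave 5.8-6.0% at 5% missing, 6.8-7.2% at 10% and 7.0-10.9% at 20% under averaging. Across all its settings, up to 30% missing, Rubin's rules gave 4.3-5.6%. Monte Carlo error is about 0.35 percentage points around 5%.

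**The case against.** Several limits stand.

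- **Inflation is conditional.** It arises only if the averaging sentence is the one followed. An analyst who follows the closing sentence and pools five analyses gets none. The SAP has not settled on the invalid method; it has failed to choose.
- **The effect is small where imputation first applies.** Just above 5% missing, type I error is about 5-6%. The 10% and 20% rows are two and four times the 5% dropout planned in section 2.3, before any substitution of another visit, so they are stress cases.
- **The percentages are illustrative.** Section 6.1.1 plans a mixed-effects model over five visits, which was not simulated.
- **Questionnaires were not simulated.** Where only some components are missing, the effect on the total score is diluted. The direction carries over; no size can be given.

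A reader might also infer that the trigger sits exactly at the planned dropout, so that chance decides the method. The documents do not support this. Section 2.3 counts all dropout, whereas section 6.6.2 counts what is missing under other circumstances, after another visit's CDAI has been substituted. Dropouts with a usable value at another visit leave the count.

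Nor do the results show that five imputations are too few: Rubin's rules with five already hold about 5%.

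What the objection does not remove is the contradiction. Nor can the averaging sentence be read as loose wording for pooling. It speaks of replacing values and chooses mean or median by each variable's distribution, which describes filling in data, not combining estimates.

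**Conclusion.** Section 6.6.2 is wrong as written. It sets two incompatible rules for the same missing data, and one of them understates uncertainty. That conclusion rests on the text alone.

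The size depends on the rule followed and on an unknown missing share. With 45 per group, a t-test and an assumed correlation of 0.3 to 0.7, averaging takes type I error to about 5-6% just above the trigger, 6-8% at 10% missing and 8-11% at 20%. The direction is general; the exact figures for the planned mixed model are not established.

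**What to change.** Three wording changes in section 6.6.2, made before unblinded analysis:

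1. Delete the sentence that replaces missing values by the mean or median of the imputations.
2. State that each imputed dataset is analysed separately with the planned model, and that estimates and variances are combined by Rubin's rules.
3. State that the same applies to the questionnaire component scores: impute components, score and analyse within each imputed dataset, then pool.

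The cost is SAP wording only. More than five imputations would be a modest, optional improvement. Curing the defect does not require removing the 5% trigger. It also does not require making the likelihood-based model the sole handling of missing data. That larger change would first have to be reconciled with the rule that substitutes another visit's CDAI.
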